### 7.2.2 Research Assays

Plasma and urine samples will be analyzed to determine concentrations of VT-1598 and VT-11134 using validated liquid chromatography/tandem mass spectrometry methods by the bioanalytical contractor, ICON BAL.

### Analytical Sample Collection and Handling

Blood samples for the determination of VT-1598 and VT-11134 plasma concentrations will be collected as shown in Table 2:

**Table 2: Blood PK Sampling Timepoints**

Blood Sampling Timepoints for VT-1598 and VT-11134 Pharmacokinetic Analyses											
Day 1 (pre-dose)	Cohorts 1-5 (fasting): Taken within 60 minutes prior to dosing										
	Cohort 6 (fed): Taken within 30 minutes prior to start of pre-dose meal.										
Day 1 (hours post dose*)	0.5	1	1.5	2	3	4	6	8	10	12	14
Day 2 (hours post dose**)	24	36									
Day 3 (hours post dose**)	48	60									
Day 4 (hours post dose**)	72										
Day 7 (hours post dose)***	144										
Day 14 (hours post dose)***	312										
Day 21 (hours post dose)***	480										

\*The 0.5-hour post dose blood sample should be taken within  $\pm 5$  minutes of the nominal timepoint. The remaining post dose blood samples on Day 1 should be taken within  $\pm 10$  minutes of the nominal time points.

\*\*The post dose blood samples during the inpatient stay should be taken within  $\pm$  30 minutes of the nominal time point on Days 2, 3 and 4.

\*\*\*For outpatient visits, blood samples should be taken within the visit window.

The exact dates and times of blood collection must be recorded in the eCRF and source documents. The blood samples will be obtained via direct venipuncture or via indwelling intravenous catheter using saline flushes to maintain catheter patency. Specific details for blood sample collection, process blood to plasma, and sample handling are included in the MOP for this study.

Urine samples for the determination of VT-1598 and VT-11134 amounts will be collected in the intervals shown in Table 3:

**Table 3: Urine PK Sampling Timepoints**

Urine Sampling Timepoints for VT-1598 and VT-11134 Pharmacokinetic Analyses			
Day 1 (pre-dose)	Collected from -6 hours until 0 hours pre-dose (For fasted cohorts)		
Day 1 (hours post dose)	0-6	>6-12	>12-24
Day 2 (hours post dose)	24-36	36-48	
Day 3 (hours post dose)	48-60	60-72	

The exact dates, start and stop time for each intervals and volumes of urine collection must be recorded in the eCRF and source documents. For each interval, volume will be measured, and an aliquot will be retained and analyzed for the determination of VT-1598 urine concentrations. Specific details for urine specimen collection and handling are included in the MOP for this study.

### Laboratory Specimen Preparation, Handling, and Storage

Detailed instructions for plasma and urine specimen preparation, handling and storage are outlined in the MOP for this study.

### Total Blood Volume Drawn

The total volume of blood that will be drawn from each subject is described in Table 4.

**Table 4: Total Volume of Blood Drawn From Each Subject**

Type	Laboratory Test	Sample Volume (mL)	Number of Samples	Total Volume (mL)

Safety:			
Clinical chemistry	3.5	7	24.5
Cortisol	3.5	7	24.5
Hematology	2	7	14
Coagulation	2.7	7	18.9
Serology	4	1	4
future assays[a]	6	1	6
Pharmacokinetic:	3	20	60
When using an indwelling catheter 1.0 mL of blood will be removed prior to sample collection			
Total	24.7	50	151.9
[a] EDTA Blood sample will be collected 6 hours post-dose; plasma will be processed and stored to allow for the option to test for additional parameters. See Section 9.3 Consent for Future Use and Storage of Specimens.			

### Laboratory Specimen Shipping

All PK and future use specimens will be shipped to the Fisher Biorepository for storage and/or transfer to the ICON BAL. Detailed instructions for shipping plasma and urine samples are outlined in the MOP for this study.

## 8 ASSESSMENT OF SAFETY

### 8.1 Assessing and Recording Safety Parameters

Safety will be assessed by collection of AEs, physical examinations, clinical laboratory results, vital signs, and ECG from time of dosing until final visit.

#### 8.1.1 Adverse Events (AEs)

ICH E6 defines an AE as any untoward medical occurrence in a patient or clinical investigation subject administered a pharmaceutical product regardless of its causal relationship to the study treatment. An AE can therefore be any unfavorable and unintended sign (including an abnormal laboratory finding), symptom, or disease temporally associated with the use of a medicinal (investigational) product. The occurrence of an AE may come to the attention of study personnel during study visits and interviews of a study recipient presenting for medical care, or upon review by a study monitor.

All adverse events should be captured on the appropriate eCRF. Information to be collected includes event description, date of onset, clinician's assessment of severity, relationship to study product (assessed only by those with the training and authority to make a diagnosis and listed on the Form FDA 1572 as an investigator) date of resolution/stabilization of the event, outcome and severity. All AEs occurring while in study must be documented appropriately regardless of relationship. All AEs will be followed to resolution/stabilization.

Any medical or laboratory condition that is present at the time that the subject is screened up through ingestion of the dose should be considered as baseline/pre-existing condition and not reported as an AE. However, if it deteriorates at any time during the study after ingestion of the dose, it should be recorded as an AE.

#### Adverse Events Grading

AEs will be assessed by a licensed study physician listed on the Form FDA 1572 as the site principal investigator or appropriate sub-investigator using a protocol-defined grading system. For events not included in the protocol-defined grading system ([Section 8](#) Assessment of Safety/[Appendix B](#) VT-1598 Toxicity Grading Criteria for Normal Human Subjects), the following guidelines will be used to quantify severity:

- Mild (Grade 1): Events require minimal or no treatment and do not interfere with the subject's daily activities;

- 
- Moderate (Grade 2): Events result in a low level of inconvenience or concern with therapeutic measures. Moderate events may cause some interference with functioning and daily activities and use of over the counter medication;
  - Severe (Grade 3): Events interrupt the subject's usual daily activities and may require systemic drug therapy or other treatment. Severe events are usually incapacitating.

**Relationship to Study Products:** The assessment of the relationship of an AE to the administration of study product is made only by those with the training and authority to make a diagnosis and listed on the Form FDA 1572 as an investigator based on all available information at the time of the completion of the eCRF. Whether the AE is related or not, is not a factor in determining what is or is not reported in this trial. If there is any doubt as to whether a clinical observation is an AE, the event should be reported.

In a clinical trial, the study product must always be suspect. To help assess, the following guidelines are used.

- Related – There is a reasonable possibility that the study product caused the adverse event. Reasonable possibility means that there is evidence to suggest a causal relationship between the study product and the adverse event;
- Not Related – There is not a reasonable possibility that the administration of the study product caused the event.

## 8.2 Serious Adverse Events (SAEs)

An adverse event or suspected adverse reaction is considered “serious” if, in the view of either the investigator or sponsor, it results in any of the following outcomes:

- Death;
- a life-threatening adverse event;
- inpatient hospitalization or prolongation of existing hospitalization;
- a persistent or significant incapacity or substantial disruption of the ability to conduct normal life functions, or;
- a congenital anomaly/birth defect;
- important medical events that may not result in death, be life-threatening, or require hospitalizations may be considered serious when, based upon appropriate medical judgment they may jeopardize the patient or subject and may require medical or surgical intervention to

---

prevent one of the outcomes listed in this definition. Examples of such medical events include allergic bronchospasm requiring intensive treatment in an emergency room or at home, blood dyscrasias or convulsions that do not result in inpatient hospitalization, or the development of drug dependency or drug abuse.

 Life-threatening adverse event. An adverse event is considered “life-threatening” if, in the view of either the site principal investigator or sponsor, its occurrence places the patient or subject at immediate risk of death. It does not include an adverse event, had it occurred in a more severe form, might have caused death.

SAEs will be:

- Assessed for severity and relationship to study product and alternate etiology (if not related to study drug);
- recorded on the appropriate SAE data collection form and eCRF;
- followed through resolution;
- reviewed and evaluated by an Independent Safety Monitor (ISM) (as deemed necessary), the SMC (periodic review unless related), DMID, and the IRB;

SAEs will be followed until resolution even if this extends beyond the study-reporting period. Resolution of an AE/SAE is defined as the return to pretreatment status or stabilization of the condition with the expectation that it will remain chronic.

## 8.3 Specification of Safety Parameters

### 8.3.1 Dose Escalation Criteria

The initial cohort of 8 subjects will be administered 40 mg of VT-1598 (6 subjects) or placebo (2 subjects) as a single oral dose. Two sentinel subjects will be included in Cohorts 1-5 as described in [Section 4.2](#) Acquisition/Distribution.

Dose escalation to each successive cohort of subjects will occur if none of the predefined dose escalation halting criteria are met (for all subjects through Day 7). Emmes will provide notification to the PI upon analysis of data for the cohort (for all subjects through Day 7) for halting criteria as described in [Section 3](#) Study Design, Objectives and Endpoints or Outcome Measures, Dose Escalation. If any of the criteria for dose escalation are met, or, at the discretion of the PI or DMID Medical Monitor, the study enrollment and dosing will be stopped until the

---

SMC reviews the data and provides its recommendations. There will be a scheduled SMC data review meeting prior to start of Cohort 5.

The nominal dose- escalation scheme will be 40, 80, 160, 320 and 640 mg) or matching placebo administered in a fasting state. The effect of a high-fat, high-calorie meal on the PK of VT-1598 is planned in an additional cohort that will be dosed at 160 mg. The fed cohort will be dosed at 160 mg, after the 320 mg fasted cohort has been dosed. This provides additional safety data to cover the possibility that the bioavailability of VT-1598 is increased in the presence of food under the fed state. The highest proposed dose in this study is 640 mg, which is 53% of the body surface area equivalent of the NOAEL in the most sensitive species.

### **8.3.2 Reporting Serious Adverse Events**

Any AE that meets a protocol-defined serious criterion must be submitted immediately (within 24 hours of site awareness) on an SAE form to the DMID Pharmacovigilance Group, at the following address:

### **8.3.3 Regulatory Reporting for Studies Conducted Under DMID-Sponsored IND**

Following notification from the investigator, DMID, the Investigational New Drug (IND) sponsor, will report any suspected adverse reaction that is both serious and unexpected. DMID will report an adverse event as a suspected adverse reaction only if there is evidence to suggest a causal relationship between the drug and the adverse event. DMID will notify FDA and all participating investigators (i.e., all investigators to whom the sponsor is providing drug under its IND(s) or under any principal investigator's IND(s) and NQP 1598, Ltd. in an IND safety report of potential serious risks from clinical trials or any other source, as soon as possible, but in no case later than 15 calendar days after the sponsor determines that the information qualifies for reporting as specified in 21 CFR Part 312.32. DMID will also notify FDA of any unexpected fatal or life-threatening suspected adverse reaction as soon as possible, but in no case later than 7 calendar days after the sponsor's initial receipt of the information. Relevant follow up information to an IND safety report will be submitted as soon as the information is available. Upon request from FDA, DMID will submit to FDA any additional data or information that the agency deems necessary, as soon as possible, but in no case later than 15 calendar days after receiving the request.

All serious events designated as "not related" to study product(s), will be reported to the FDA at least annually in a summary format.

### **8.3.4 Reporting of Pregnancy**

A Notification of Pregnancy form will be completed for any female study subject or for any female partner of a male study subject who becomes pregnant following their exposure to study product (Day 1) through 3 months after the dose of study product. The site will discuss pregnancy reporting with subjects at the Final Study visit with instructions and provide contact information in case pregnancy occurs. The pregnant subject will be followed by monthly telephone calls until 2 months after the birth of the baby or until the end of the pregnancy (in case pregnancy is terminated) at which time the Pregnancy Outcome form will be completed. Infants born to these study subjects will also be monitored for SAEs for up to 2 months after birth (information regarding SAEs will be captured on the Pregnancy Outcome form and the SAE form). If an SAE occurs during the pregnancy, the SAE will be reported on the appropriate SAE form and provided to DMID pharmacovigilance. Pregnancy Outcome forms will be used to collect, but not be limited to, data on the following information, should it be identified during the monthly telephone calls, at the end of the pregnancy, or at the follow-up telephone call at 2 months after birth of the baby:

1. Prior maternal history including congenital abnormalities or pregnancy complications;
2. estimated date of conception;
3. estimated and actual date of delivery or pregnancy termination;
4. mode of delivery;
5. maternal complications;
6. neonatal complications (i.e. lethal or nonlethal congenital abnormality).

## **8.4 Type and Duration of Follow-up of Subjects after Adverse Events**

All AEs will be followed until resolution even if this extends beyond the study-reporting period. Resolution of an AE/SAE is defined as the return to pretreatment status or stabilization of the condition with the expectation that it will remain chronic.

## **8.5 Procedures to be Followed in the Event of Abnormal Laboratory Test Values or Abnormal Clinical Findings**

Abnormal laboratory values, performed as part of hematology, chemistry panel, or urinalysis but not listed in [Appendix B](#), VT-1598 Toxicity Grading Criteria for Normal Human Subjects, will be evaluated by the study clinicians, recorded in the source document and, if clinically significant, considered AEs and graded according to the criteria details described in [Section 8.1](#) Assessing and Recording Safety Parameters.

The site principal investigator or appropriate sub-investigator is responsible for recording all AE and SAEs that are observed or reported during this study, regardless of the relationship to study product. AE and SAEs or abnormal clinical findings will be collected, assessed, documented, reported, and followed appropriately.

## **8.6 Halting Rules**

### **8.6.1 Study Halting Criteria**

If any of the criterion below are met, the study will be suspended (enrollment and dosing), and the SMC ad hoc meeting will convene:

- Any SAE, regardless of the relationship to the study drug, throughout duration of study, unless confirmed to be of reasonable alternative etiology.

- 
- 5 or more subjects in study (cumulative among all cohorts) experience a same grade 2 (or higher) related AE (laboratory or systemic) which is coded in the same high-level group term (HLGT) per MedDRA coding, throughout duration of study.

## 8.6.2 Dose Escalation Halting Criteria

### Sentinel Subject Halting Rules

If any of the criterion below are met, the cohort will be suspended (enrollment and dosing), and the SMC ad hoc meeting will convene:

- Any SAE (regardless of the relationship to the study drug) through Day 3 of the study;
- any Grade 2 (or higher) adverse event (laboratory or systemic) if not resolved within 1 day, through Day 3 of the study.

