**Table 1: Single Dose\* Escalation**

Cohort 1 - fasting	6 subjects**	Single 40 mg VT-1598 tablet	Safety data for Cohort 1 subjects through Day 7 will be confirmed by reviewing objective pre-defined criteria before continuing to Cohort 2.
	Dose: 40 mg	2 subjects**	
Cohort 2 - fasting	6 subjects**	Two 40 mg VT-1598 tablets	Safety data for Cohort 2 subjects through Day 7 will be confirmed by reviewing objective pre-defined criteria before continuing to Cohort 3.
	Dose: 80 mg	2 subjects**	
Cohort 3 - fasting	6 subjects**	Four 40 mg VT-1598 tablets	Safety data for Cohort 3 subjects through Day 7 will be confirmed by reviewing objective pre-defined criteria before continuing to Cohort 4 and 6. Interim analysis of PK data (Cohorts 1-3)***
	Dose: 160 mg	2 subjects**	
Cohort 4 – fasting	6 subjects**	Four 80 mg VT-1598 tablets	Cumulative safety data for all subjects in Cohorts 1-4 through Day 21 will be reviewed by the SMC for recommendation/confirmation of dosing before continuing to Cohort 5
	Dose: 320 mg	2 subjects**	
Cohort 5 – fasting	6 subjects**	Eight 80 mg VT-1598 tablets	
	Dose: 640 mg	2 subjects**	
Cohort 6 – fed (high-fat, high- calorie meal)	6 subjects	Four 40 mg VT-1598 tablets	Cohort 6 is comprised of the same subjects as Cohort 3****. These subjects will receive the same treatment in Cohort 6 as Cohort 3. Cohort 6 may start enrolling prior to convening the SMC meeting and prior to the start of Cohort 5.
	Dose: 160 mg	2 subjects	

[figure not shown]
\*Dose refers to the free base equivalent of the drug.

\*\*Within each fasted cohort two sentinel subjects will be admitted initially, and the randomization scheme will be designed to ensure that one subject will receive VT-1598 and the other will receive placebo. All sentinel subject safety data through Day 3 is reviewed by PI prior to dosing remainder of cohort.

\*\*\*PK data only; enrollment for Cohort 4 will not stop for the PK interim analysis.

\*\*\*\* The Cohort 6 replacement subjects will receive the same treatment as assigned to the Cohort 3 subject they are replacing.

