### **3.2.3 Study Endpoints or Outcome Measures**

#### **3.2.4 Primary Outcome Measures**

- Safety will be evaluated for single-ascending fasting oral doses of VT-1598. Safety will be assessed by adverse events from start of dosing to Day 21, clinical laboratory tests at baseline and from Day 4 to Day 21, ECGs at baseline and on Day 4 and Day 21, and vital signs at baseline and from Day 1 to Day 21;
- Safety will be evaluated for single oral dose of VT-1598 administered after being fed a high-fat, high calorie meal. Safety will be assessed by adverse effects from start of dosing to Day 21, clinical laboratory tests at baseline and from Day 4 to Day 21, ECGs at baseline and vital signs at baseline and from Day 1 to Day 21.

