### 6.3.1 Day 2 – Inpatient CRU

Subjects are inpatients in the CRU and will undergo procedures as indicated in the Schedule of Study Procedures and Evaluations ([Appendix A](#) VT-1598 Schedule of Study Procedures and Evaluations) and as detailed in [Section 7](#) Description of Clinical and Laboratory Evaluations, Study Procedures/Evaluations: listed below:

- Review and record any concomitant medications and non-pharmacologic treatments/procedures since Day 1;
- obtain blood samples for PK analysis at 24 h ( $\pm 30$  min), and 36 h ( $\pm 30$  min) post-dose;

- 
- collect urine samples for PK analysis in the following intervals following study product administration on Day 1: 24-36, 36-48 hours post-dose;
  - obtain resting vital signs (heart rate, blood pressure, oral temperature and respiration rate, taken after being at rest for at least 5 minutes) at 24 h ( $\pm 30$  min), post-dose. If abnormal, these measurements may be repeated once, within 15 minutes of the original assessment;
  - collect and record adverse events (AEs).

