### 6.3.2 Day 3 – Inpatient CRU

Subjects are inpatients in the CRU and will undergo procedures as indicated in the Schedule of Study Procedures and Evaluations ([Appendix A](#) VT-1598 Schedule of Study Procedures and Evaluations) and as detailed in [Section 7](#) Description of Clinical and Laboratory Evaluations. Study Procedures/Evaluations: listed below:

- Review and record any concomitant medications and non-pharmacologic treatments/procedures since Day 2;
- obtain blood sample for PK analysis at 48 h ( $\pm 30$  min) and 60 h ( $\pm 30$  min) post-dose;
- collect urine sample for PK analysis in the following interval following study product administration on Day 1: 48-60 hours post-dose;
- obtain resting vital signs (heart rate, blood pressure, oral temperature and respiration rate, taken after being at rest for at least 5 minutes) at 48 h ( $\pm 30$  min), post-dose. If abnormal, these measurements may be repeated once, within 15 minutes of the original assessment;
- collect and record adverse events (AEs).

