### 6.3.3 Day 4 – Discharge from CRU

Subjects are inpatients in the CRU and will undergo procedures as indicated in the Schedule of Study Procedures and Evaluations ([Appendix A](#) VT-1598 Schedule of Study Procedures and Evaluations) and as detailed in [Section 7](#) Description of Clinical and Laboratory Evaluations. Study Procedures/Evaluations: listed below, prior to discharge from CRU:

- Review and record any concomitant medications and non-pharmacologic treatments/procedures since Day 3;
- obtain blood sample for PK analysis at 72 h ( $\pm 30$  min) post-dose;

- 
- collect urine sample for PK analysis in the following interval following study product administration on Day 1: 60-72 hours post-dose;
  - obtain blood samples for fasting (at least 8 hours and prior to 10 AM ) clinical chemistry, hematology, and coagulation tests;
  - obtain urine sample for urinalysis;
  - targeted physical examination (general appearance, heart, lungs, skin and abdomen) including resting vital signs (heart rate, blood pressure, oral temperature and respiration rate, taken at 72 hours ( $\pm 30$  min) post-dose and after being at rest for at least 5 minutes). If abnormal, these measurements may be repeated once, within 15 minutes of the original assessment;
  - 12-lead ECGs obtained after at least 5 minutes in the supine position; taken at 72 hours ( $\pm 30$  min) post-dose; triplicate readings, at least 1 minute apart within a 15-minute period;
  - collect and record adverse events (AEs);
  - review post-discharge instructions (including birth control methods, permitted/non-permitted medications, non-medications, dietary and activity restrictions), and schedule follow-up visits;
  - discharge from CRU.

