4. INVESTIGATIONAL PLAN

4.1. Overall Study Design and Plan

This is a Phase 1, randomized, double-blind, placebo-controlled, SAD study in healthy adult subjects. It is designed to evaluate the safety and PK of single oral doses of VT-1598. An overall schematic of study design is shown in [Figure 1](#). A flowchart of subject disposition will be shown in [Figure 2](#), and a table showing all planned study cohorts and dose levels can be found in [Table 1](#). There will be 5 fasted cohorts: 40 mg VT-1598 or matching placebo, 80 mg VT-1598 or matching placebo, 160 mg VT-1598 or matching placebo, 320 mg VT-1598 or matching placebo, 640 mg VT-1598 or matching placebo, and one fed cohort: 160 mg VT-1598 or matching placebo following a high-fat, high-calorie meal.

A maximum of 40 subjects at a single site will be enrolled in the study to one of the fasted cohorts (Cohorts 1-5). Within each fasted cohort, a total of 8 subjects will be randomized 3:1 to receive active drug (VT-1598) (6 subjects) or placebo (2 subjects). For Cohort 1 through Cohort 5, the first 2 subjects will be randomized 1:1 to receive active drug or placebo to ensure that 1 of the first 2 subjects receives active drug and the other receives placebo for sentinel dosing. The study product assignment of the remaining 6 subjects in each of the fasted cohorts (Cohorts 1-5) will be randomly assigned 5:1 active drug to placebo to maintain the 3:1 ratio for the entire cohort. All sentinel subject safety data through Day 3 will be reviewed by the Principal Investigator (PI) prior to dosing the remaining 6 subjects in each fasted cohort.

Subjects who complete Cohort 3 and do not early terminate from the study will have enrollment “rollover” to Cohort 6, the fed cohort, after a minimum of 60 days for a “wash-out” period. Cohort 3 subjects continuing to Cohort 6 will not be randomized but will receive the same study product and dose as they received in Cohort 3 (160 mg VT-1598 or matching placebo) following a high-fat, high-calorie meal. Furthermore, there will be no sentinel subjects in Cohort 6. Cohort 3 subjects that are no longer eligible for the trial after the wash-out period will be replaced ([Section 4.4.3](#)). Subjects replacing individuals from Cohort 3 who did not continue on to Cohort 6 will not be randomized and will receive the same study product assignment as the Cohort 3 subject they are replacing.

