9.1 Overall Study Design and Plan Description

Table 1: Study Design

Cohort	Dose ^a (mg)	Fasting Status	VT-1598		Placebo		Cohort Comments
			Number of Subjects ^b	Study Product	Number of Subjects ^b	Study Product	
1	40	Fasted	6	Single 40 mg VT-1598 tablet	2	Single 40 mg matching Placebo	Safety data for Cohort 1 subjects through Day 7 will be confirmed by reviewing objective pre-defined criteria before continuing to Cohort 2.
2	80	Fasted	6	Two 40 mg VT-1598 tablets	2	Two 40 mg matching Placebo	Safety data for Cohort 2 subjects through Day 7 will be confirmed by reviewing objective pre-defined criteria before continuing to Cohort 3.
3	160	Fasted	6	Four 40 mg VT-1598 tablets	2	Four 40 mg matching Placebo	Safety data for Cohort 3 subjects through Day 7 will be confirmed by reviewing objective pre-defined criteria before continuing to Cohorts 4 and 6. Interim analysis of PK data (Cohorts 1-3) ^c .
4	320	Fasted	6	Four 80 mg VT-1598 tablets	2	Four 80 mg matching Placebo	Cumulative safety data for all subjects in Cohorts 1-4 through Day 21 will be reviewed by the SMC for recommendation/confirmation of dosing before continuing to Cohort 5.
5	640	Fasted	6	Eight 80 mg VT-1598 tablets	2	Eight 80 mg matching Placebo	
6	160	Fed	6	Four 40 mg VT-1598 tablets	2	Four 40 mg matching Placebo	Cohort 6 is comprised of the same subjects as Cohort 3. ^d These subjects will receive the same study product in Cohort 6 as Cohort 3, following a high-fat, high-calorie meal. Cohort 6 may start enrolling prior to convening the SMC meeting and prior to the start of Cohort 5.

^aDose refers to the free base equivalent of the drug.

^bWithin each fasted cohort, two sentinel subjects will be admitted initially, and the randomization scheme will be designed to ensure that one subject will receive VT-1598 and the other will receive placebo. All sentinel subject safety data through Day 3 is reviewed by PI prior to dosing the remainder of the cohort.

^cPK data only. Enrollment for Cohort 4 will not stop for the PK interim analysis.

^dThe Cohort 6 replacement subjects will receive the same treatment as assigned to the Cohort 3 subject they are replacing.

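### The laboratory part of the sentinel halting rule has no scheduled data behind it: the rule cuts off at Day 3 and the first post-dose safety panel is on Day 4

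*Protocol*

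**What the plan says.** Each fasted cohort starts with two sentinels, one on active drug and one on placebo. Under the sentinel rules in Protocol 8.6.2, the cohort is suspended and the SMC convened for any SAE through Day 3, or for "any Grade 2 (or higher) adverse event (laboratory or systemic) if not resolved within 1 day, through Day 3 of the study". Relatedness is not required.

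The PI review has the same cut-off. The Protocol Table 1 footnote says "All sentinel subject safety data through Day 3 is reviewed by PI prior to dosing remainder of cohort". SAP 4.1 says "All sentinel subject safety data through Day 3 will be reviewed by the Principal Investigator (PI) prior to dosing the remaining 6 subjects", and the footnote to SAP Table 1 repeats it.

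Protocol 3.1.2 adds a minimum wait of three days before the next six subjects are dosed, but that sentence names only Cohorts 2-5.

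The laboratory schedule starts later. Protocol 3.2.4 lists "clinical laboratory tests at baseline and from Day 4 to Day 21". Section 6.3.3 places the first post-dose panel on Day 4: "obtain blood samples for fasting (at least 8 hours and prior to 10 AM ) clinical chemistry, hematology, and coagulation tests", with urinalysis at the same visit.

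**The concern.** The sentinel step exists so that an early signal in one subject can stop the rest of a cohort from receiving a dose level not yet given to humans. The rule expressly includes laboratory events, and one sentinel is enough to trigger it. With the window closing a study day before the first panel, that part of the rule cannot fire from planned data.

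The people affected are the remaining six in the same cohort, five on active drug and one on placebo. Subjects at the next dose level are better covered, because the cohort rule runs through Day 7 and so takes in the Day 4 and Day 7 panels.

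Prothrombin time and PTT show the kind of finding involved. Protocol 2.3.1 reports both as prolonged in the animal toxicity studies, and Appendix B grades both.

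**Working it through.** **1. Does Day 3 include 72 h?** No. SAP 3.3.5 makes the dosing day Study Day 1. The protocol puts the 48 h and 60 h samples on Day 3 and the 72 h sample on Day 4.

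**2. What is scheduled inside the window?** From Protocol 6.3 and Appendix A, post-dose:

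| Study day | Safety panel | Vital signs | ECG | Blood drawn for |
|---|---|---|---|---|
| 1 | none | 1, 2, 4, 8 h | 4 h | PK; one optional future-use sample |
| 2 | none | 24 h | none | PK |
| 3 | none | 48 h | none | PK |
| 4 | chemistry, hematology, coagulation, urinalysis | 72 h | 72 h | PK and safety |

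The Day 2 and Day 3 entries read "obtain blood samples for PK analysis at 24 h" and "obtain blood sample for PK analysis at 48 h"; neither day lists a safety sample. Scheduled post-dose panels are on Days 4, 7, 14 and 21.

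- Inside Days 1-3: 0 of 4.
- If the window included Day 4: 1 of 4.
- Inside the cohort rule's window, through Day 7: 2 of 4.

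The rest of the sentinel rule does have input: adverse event collection, 6 vital-sign times and 1 ECG time.

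Protocol Table 4 budgets seven chemistry, hematology and coagulation samples against six scheduled visits (Screening, Day -1, Days 4, 7, 14, 21). The seventh matches the Unscheduled column of Appendix A. Nothing places it on Days 1-3.

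**3. Would another predefined rule catch one sentinel's non-serious Grade 2 value on Day 4?**

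- Cohort rule (8.6.2): needs at least 2 subjects with the same related event. 1 < 2, so no.
- Study rule (8.6.1): needs at least 5 such subjects. 1 < 5, so no.
- Cortisol (7.2.1): a Grade 2 or higher value must be repeated and, if confirmed, leads to an ACTH test, but no hold on dosing is stated.

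**4. Will the Day 4 sample exist before the other six are dosed?** Take three days as 72 h. Protocol 3.1.2 has the six admitted after the wait, and 6.2.1 puts admission about 24 h before dosing. Then 72 + 24 = about 96 h, and 96 - 72 = about 24 h after the Day 4 sample. Laboratory turnaround is not stated. This sequence is explicit for Cohorts 2-5. Cohort 1 has the PI review but no stated wait.

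**5. What would automatic suspension cost?** The documents give no background rate. Assume each sentinel independently has a 5% or 10% chance of a persisting background Grade 2 or higher value.

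| | 5% | 10% |
|---|---|---|
| A cohort (2 sentinels) is suspended | 1 - 0.95^2 = 9.75% | 1 - 0.90^2 = 19.0% |
| At least one suspension in five cohorts (10 sentinels) | 1 - 0.95^10 = 40.1% | 1 - 0.90^10 = 65.1% |

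**The case against.** The strongest reply is that the practical gap is small. The Day 4 sample is normally drawn about a day before the other six are dosed. An abnormal laboratory finding can be an adverse event and must then be recorded. Protocol 8.3.1 lets the PI or the medical monitor stop dosing on their own judgment, 8.7.2 lets DMID call an ad hoc SMC meeting, 6.7 allows unscheduled tests, and an event may be judged serious. Three days is a minimum. An event starting on Day 3 can be called unresolved only with information from the following day, so the decision already comes after Day 3.

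Much of that stands. A reader might infer that sentinels go unmonitored for three days, that the six are dosed before any laboratory sample is taken, or that a bad Day 4 result would be ignored. The documents support none of these. But every route listed is discretionary, while Protocol 3.1.2 describes the sentinel criteria as objective and set in advance. None of them makes a value first seen on Day 4 count, and neither document requires the result to be in hand.

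It is also fair to say that the laboratory wording recurs in all three halting rules and could be meant here for clinically prompted tests. That reading is workable, but it leaves the laboratory part dependent on someone deciding to order a test.

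The reply is right about automatic suspension. The rule ignores relatedness and counts the placebo sentinel. Some Appendix B bands are narrow (high sodium is Grade 1 at 144-145 and Grade 2 at 146-147 mEq/L), and most Grade 1 values are allowed at entry. Leaving an isolated value to clinical judgment is defensible.

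**Conclusion.** The mismatch is confirmed: 0 of 4 scheduled post-dose panels fall in the sentinel window, and the first comes one study day after it closes. The laboratory part can be triggered only by an unscheduled test, and the response to a single sentinel's non-serious Grade 2 or higher value on Day 4 is discretionary. The gap is confined to the cohort being dosed.

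This is a worthwhile, low-cost improvement. The documents do not show that harm is likely. One might read the coagulation findings as a prediction of trouble by 72 h, but they come from general toxicity studies, with repeat-dose studies of up to 28 days, and nothing here shows a single-dose effect by then. The starting dose carries a 28-fold margin, and the top dose is put at 53% of the rat NOAEL scaled by body surface area. Nor do the documents settle that an unresolved Day 4 value should halt the cohort by itself; at the assumed rates, background values would suspend about 10% to 19% of cohorts.

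The count is firm. How Day 4 results are handled in practice is less certain, because the MOP, which also holds dosing details, and the SMC charter were not available.

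**What to change.** In Protocol 8.6.2, 3.1.2 and the Table 1 footnote:

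- extend the sentinel review to include the Day 4 safety laboratory results;
- require the PI to review those results before the remaining six subjects are dosed;
- state that the wait applies to Cohorts 1-5.

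The sponsor should also state what an unresolved Grade 2 or higher Day 4 value does: suspend the cohort automatically, or only if judged related or clinically significant. Either way, a repeat sample about a day later, taken as an unscheduled test under 6.7, would show whether the value has resolved.

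No new scheduled panel is needed. The cost is up to about one day's delay per cohort and an occasional repeat draw on about Day 5, after discharge. If the sponsor chooses automatic suspension, the background suspensions above are added.

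The change applies to cohorts not yet dosed. SAP section 15 already reports who returned for Cohort 6, so for completed cohorts this can only be a matter of reporting. The SAP needs no analysis change and should describe the review as it was done. The study report could say whether Day 4 sentinel results were seen before the remaining six were dosed.
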